6.4 Study Discontinuation and Stopping Criteria

6.4.1 Dose Escalation Stopping Criteria

Dose escalation will be stopped if one of the following conditions apply:

• Death of a subject (AE grade 5 toxicity) in one cohort, at any time, that is considered related to the IP, judged by the Investigator

- One subject in a cohort develops an AE ≥ Grade 3 toxicity, that is considered related to the IP, judged by the Investigator
- One subject in a cohort develops an AE Grade 2 toxicity that persists for more than 7 days and is considered related to the IP, judged by the Investigator
- 2 or more of the subjects in a cohort have experienced severe adverse events, judged to be possibly or probably related to the IP, judged by the Investigator;
- 2 or more subjects receiving HM15211 develop similar clinically significant laboratory, significant ECG or vital signs abnormalities, or severe AEs in the same organ class, indicating dose-limiting intolerance. Dose escalation may proceed if after review of the data by the Investigator and discussion with Sponsor, it is concluded that the events are not drug related;
- It is determined that the limit of safety and/or tolerability has been reached. Decision will be made between Sponsor and Investigator.

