10.3 Relationship to Study Treatment

The relationship of each AE to the study drug(s) will be assessed by the Investigator or Sub-Investigator on the basis of his/her clinical judgment and the following definitions:

1= Related:

The AE follows a reasonable temporal sequence from the study product administration, and cannot be reasonably explained by the subject's clinical state or other factors (e.g., disease under study, concurrent diseases, or concomitant medications).

The AE follows a reasonable temporal sequence from the investigational product administration, and represents a known reaction to the drug under study or other drugs in its class, or is predicted by the known pharmacological properties of the drug.

The AE resolves with discontinuation of the investigational product and/or recurs with rechallenge, if applicable.

2 = Not Related:

The AE does not follow a reasonable temporal sequence from investigational product administration, or can be reasonably explained by the subject's clinical state or other factors (e.g., disease under study, concurrent diseases, and concomitant medications).

3= Not Assessable/ Not Classifiable:

The AE cannot be judged because of insufficient or contradictory information. The AE cannot be supplemented or verified.

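### Stops 1 to 3 in section 6.4.1 need an event considered related, and the protocol does not say how a Not Assessable event counts, so one such death or Grade 3 or higher AE appears to trigger no mandatory stop

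*Protocol*

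**What the plan says.** Section 6.4.1 of the protocol lists six conditions and says escalation will be stopped if one applies. They are numbered here in the order printed.

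- Stop 1: "Death of a subject (AE grade 5 toxicity) in one cohort, at any time, that is considered related to the IP".
- Stop 2: one subject in a cohort with an AE at or above "Grade 3 toxicity, that is considered related to the IP, judged by the Investigator".
- Stop 3: one subject with a Grade 2 AE that "persists for more than 7 days and is considered related to the IP".
- Stop 4: two or more subjects in a cohort with severe AEs "judged to be possibly or probably related to the IP".
- Stop 5: two or more subjects on HM15211 with similar significant abnormalities, or severe AEs in one organ class, that point to dose-limiting intolerance. It carries a release: the Investigator looks at the data and talks with the Sponsor, and the next step is allowed when "it is concluded that the events are not drug related".
- Stop 6: a joint Sponsor and Investigator judgement that the limit of safety or tolerability has been reached, with no defined trigger.

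Section 10.3 sets the causality scale. Each AE is "assessed by the Investigator or Sub-Investigator on the basis of his/her clinical judgment and the following definitions". There are three results: Related, Not Related, and Not Assessable/Not Classifiable. The third is defined as follows: "The AE cannot be judged because of insufficient or contradictory information. The AE cannot be supplemented or verified".

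Sections 4.5 and 6.1 make every escalation a decision of the Sponsor and the Investigator after a review of safety and available PK data.

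**The concern.** The three stops that a single subject can trigger all depend on relatedness being affirmed. The causality scale has a result for events on which no judgement can be made, and the protocol does not connect the two. Read plainly, an event that cannot be judged has not been considered related, so the least documented events get the weaker default.

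Stop 5 treats open causality differently. Once its own conditions are met, escalation is held until the events are concluded not to be drug related. Stops 1 to 3 cover a death and single serious toxicities but have no such protection, and the protocol gives no reason for the difference.

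This is a first-in-human dose escalation. If the gap is reached, the next cohort's exposure rests on a discretionary review where a defined hold would be expected.

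**Working it through.** The protocol states no operating characteristic for its stopping rules and no expected rate of Not Assessable events, so there is no figure to reproduce. The check sets one event against each stop.

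**Step 1: the criteria.** Take one subject on HM15211 with one Grade 3 or higher AE. Class it Related, then Not Assessable, with all else equal.

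| Stop | Subjects needed | Attribution needed | If Related | If Not Assessable |
|---|---|---|---|---|
| 1 | 1 | considered related | met if fatal | not met, even if fatal |
| 2 | 1 | considered related | met | not met |
| 3 | 1 | considered related | does not apply (Grade 2 only) | does not apply; a persistent Grade 2 AE in this class would also not meet it |
| 4 | 2 or more | possibly or probably related | not met (1 < 2) | not met (1 < 2) |
| 5 | 2 or more on HM15211 | released only if concluded not drug related | not met (1 < 2) | not met (1 < 2) |
| 6 | none stated | joint judgement | discretionary | discretionary |

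The Related event meets stop 2. The Not Assessable event meets 0 of stops 1 to 5.

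**Step 2: what rides on it.** The dose caps in section 4.5 give 0.02/0.01 = 0.04/0.02 = 0.08/0.04 = 0.16/0.08 = 2. The next cohort is 6 active + 2 placebo = 8 subjects. Each occurrence therefore concerns 6 active subjects at up to 2 times the dose.

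**Step 3: timing.** Section 4.5 allows the decision once 6 subjects, at least 4 of them on active drug, have completed Day 10. The follow-up visit is on Day 30, so nominally 30 − 10 = 20 days of observation can remain. Section 10.6 allows an AE still unresolved at that visit to be recorded as ongoing. Information that would settle causality can therefore arrive after the next cohort has been dosed.

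**Step 4: illustration under assumptions.** Let p be the per-subject rate of drug-caused Grade 3 or higher AEs and q the share of them left Not Assessable, with subjects independent. Neither value is in the protocol. The chance that 6 active subjects trigger stop 2 is 1 − (1 − p(1 − q))^6. Setting q = 0 gives the same result as counting Not Assessable events as related.

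| p | q = 0 | q = 0.10 | q = 0.25 |
|---|---|---|---|
| 0.05 | 26.5% | 24.1% | 20.5% |
| 0.10 | 46.9% | 43.2% | 37.4% |
| 0.20 | 73.8% | 69.6% | 62.3% |
| 0.30 | 88.2% | 84.9% | 78.3% |

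The loss is 2.4 to 4.2 percentage points at q = 0.10 and 6.0 to 11.5 at q = 0.25. This is the loss of a mandatory trigger only. The review or stop 6 may still halt escalation.

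**The case against.** The strongest reply is that section 6.4.1 never refers to section 10.3. It asks what the Investigator considers, and stop 4 uses terms that are not on the 10.3 scale, so an Investigator could treat an event as related for escalation whatever its recorded class. That stands. The gap is an inference from the ordinary meaning of the two sections. Still, the only AE causality classification the protocol defines has a class for events that cannot be judged, and the reader is not told what to do with it.

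The second reply is rarity, and that stands too. Subjects are in-house until Day 7 and seen on Day 10, peak concentration is expected about 3 days after dosing, and section 10.4.1 requires AEs to be followed until they subside or are explained. Under section 10.3, an event in reasonable temporal sequence with no other reasonable explanation is already Related. Loss to follow-up is a possible route to the third class, but it fits stop 3 poorly, because persistence beyond 7 days has to be observed.

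Third, existing safeguards cover much of the ground: a positive decision before each step, stop 6, and reporting to the IRB of unexpected SAEs for which a causal link cannot be excluded. These soften the gap. They do not turn a discretionary choice into a defined hold.

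Three stronger readings are tempting, and the protocol does not support them:

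- **The next cohort would be dosed automatically after a Not Assessable death.** Sections 4.5 and 6.1 require a decision every time.
- **Stop 5 is a simple mirror image of stops 1 to 3.** It also needs two or more subjects on HM15211 and a pattern indicating dose-limiting intolerance before its release clause applies.
- **Stop 4's vocabulary causes the gap.** It is a separate, minor mismatch, and stop 4 needs two subjects in any case. Its wording might even capture some unresolved events, so stop 5 cannot be called the only two-subject route.

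**Conclusion.** The point holds as a cheap improvement to consider, with moderate confidence. Read in its ordinary sense, section 6.4.1 gives no mandatory stop for a single death, Grade 3 or higher AE, or persistent Grade 2 AE that the Investigator leaves as Not Assessable. The effect is a discretionary review where the same event classed Related would bring a defined stop.

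The conclusion rests on one assumption: that an event which cannot be judged has not been considered related. No frequency is claimed. The percentages in the working depend entirely on assumed p and q, and q should be small given the follow-up rules. The statistical analysis plan is not at hand, but criteria for stopping escalation belong in the protocol, which sets them out in section 6.4.1.

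**What to change.** Add two sentences to section 6.4.1. The first: for stops 1 to 3, an event classed Not Assessable/Not Classifiable under section 10.3 counts as related until it is resolved. The second: escalation may resume only on the terms of stop 5's existing release, that is, once the Investigator has reviewed the data, discussed them with the Sponsor, and the event has been concluded not to be drug related.

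Leave stop 4 as worded. Replacing its attribution terms with 10.3 categories could weaken it. An event with a reasonable alternative explanation is Not Related under 10.3, yet it may still be possibly related and so count towards stop 4 today.

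The text change is small and leaves sample size, visits, blinding and analysis untouched. The cost is operational: an occasional hold, possibly for an event in one of the 2 blinded placebo subjects in a cohort. Because a Not Assessable event may by definition never be clarified, the hold could be long or could end escalation. The Sponsor should accept that cost knowingly when adopting the change.

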Subjects	Healthy Obese Subjects

Number of	Approximately 40 subjects, divided in 5 cohorts with 8 subjects	
Subjects	per cohort.	
Summary of Study Design	This is a double-blind, randomized, placebo controlled, SAD study to investigate the safety, tolerability, and PK of the subcutaneous (SC) administration of HM15211 in healthy obese subjects.	
	The study will be conducted in 5 sequential dosing cohorts, enrolling 8 subjects per cohort. Cohorts may partially overlap, if dose escalation decision after the Day 10 Visit has been made. Subjects will be randomized to HM15211 or placebo in a ratio of 6:2 (6 on active, 2 on placebo).	
	Dosing will follow a sentinel approach with dosing at least 24 hours apart. Based on available safety, tolerability, and PK data, and following a safety review and dose escalation meeting between the investigator and the sponsor, dose escalation to the next cohort may proceed. If dose escalation is stopped, dose deescalation may occur in additional cohorts, to further refine clinically relevant dose levels.	
	Adjustments to the procedures may occur after the review of available safety and PK data:	
	 Adjustments to the number of study cohorts may occur: Additional cohorts may be enrolled and proceed at a higher or a lower dose. If deemed appropriate by the investigator and sponsor, there may be more than one cohort investigated at the same dose level. 	
	• Adjustments to the 24-hr BP and HR monitoring: After the evaluation of the first cohort, tests may be rescheduled, or measurement periods may be focused on specific days to capture the 24-h measurement around the PK _{peak} .	
	 Adjustments to the visit schedule: If PK data suggest, additional sampling times and/or outpatient visits may be added to the study schedule. 	
	Each subject will undergo a screening visit, up to 28 days prior to the first dosing.	
	Each subject will undergo one in-house period of 9-day duration, two outpatient visits, and a follow-up visit.	
	Screening:	

A Screening Visit will be performed up to 28 days prior to the first dosing to identify eligible subjects for the study.

In-house Period:

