4.5 Dose Escalation Algorithm

The proposed dose escalation algorithm for HM15211 may include the following steps:

Table 4-2 Sample Allocation and Dose Escalation

Cohorts	Number of Subjects	Treatment Period	
Cohort 1	N=6	HM15211- 0.01 mg/kg	
	N=2	Placebo	
Cohort 2	N=6	$HM15211 \le 0.02 \text{ mg/kg}$	
	N=2	Placebo	
Cohort 3	N=6	$HM15211 \le 0.04 \text{ mg/kg}$	
	N=2	Placebo	
Cohort 4	N=6	$HM15211 \le 0.08 \text{ mg/kg}$	
	N=2	Placebo	
Cohort 5	N=6	$HM15211 \le 0.16 \text{ mg/kg}$	
Conort	N=2	Placebo	

Each subject will be randomized to HM15211 or placebo according to the table above. The dose will be 0.01 mg/kg, based on the body weight measured prior to dosing. For dose calculation and rounding, please refer to the Operational Manual/Pharmacy Manual.

After at least 6 subjects ($n \ge 4$ subjects on active drug HM15211) in each cohort have completed at least Day 10, safety and available PK data will be reviewed and a dose decision/ dose escalation decision for the subsequent cohort will be made by the Sponsor and the Investigator. Doses between cohorts will not exceed a 2-fold increase relative to the specified doses stated in the Table 4-3 above. Following the dose escalation decision, the procedures for the subsequent cohorts will be identical to those described above.

Adjustments to the procedures/cohorts may occur after the review of available safety and PK data:

- Adjustments to the number of study cohorts may occur: Additional cohorts may
 be enrolled and proceed at a higher or a lower dose. If deemed appropriate by the
 investigator and sponsor, there may be more than one cohort investigated at the
 same dose level.
- Adjustments to the 24-hr BP and HR monitoring: After the evaluation of the first cohort, tests may be rescheduled, or measurement periods may be focused on specific days to capture the 24-h measurement around the PK_{peak}.
- Adjustments to the visit schedule: If PK data suggest, additional sampling times and/or outpatient visits may be added to the study schedule.

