6.0 STUDY DESIGN AND DESCRIPTION

6.1 Study Design

This is a first-in-human, randomized, double-blind, SAD study to evaluate the safety, tolerability, and PK of HM15211 as primary objectives in healthy obese subjects.

The study will be conducted in five sequential cohorts (cohort 1 to 5) comprising a total of up to approximately 40 subjects. Each cohort will enroll subjects to ensure that at least 8 subjects per cohort will complete the study. Drop-outs may be replaced in order to have 8 completed subjects in each cohort. Subjects will be allocated into sequential dosing cohorts based on their order of entry into the study and be randomized to investigational product (IP) or placebo in a 3:1 ratio, with 6 subjects on IP and 2 subjects on placebo. Cohorts may partially overlap after at least 6 subjects have completed at least D10 and a dose escalation decision has been made.

Dosing will follow a sentinel approach with the dosing between the first 2 subjects (1 on active, 1 on placebo) and the remainder of the cohort at least 24 hours apart. A minimum of 10-days between the start date of consecutive dose levels will be maintained. Based on available safety, tolerability, and PK data of each cohort, and following a safety review and dose escalation meeting between the investigator and the sponsor, dose escalation to the next cohort may proceed. If dose escalation is stopped (please see dose escalation stopping criteria in section 6.4.1), dose de-escalation may occur in additional cohorts, to further refine clinically relevant dose levels.

Each subject will undergo a screening visit, followed by one in-house/ treatment period per subject. Two additional outpatient visits will occur, prior to a final follow-up visit that will conclude subject study participation.

The duration of subject participation in this study, including screening, treatment and follow-up will approximately be 9 weeks for subjects.

Figure 6-1 Study Design Schematic

[figure not shown]
[figure not shown]

Figure 6-2 Dose Escalation Schematic

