6.2 Study Description

Each subject will undergo the following procedures during the study:

Screening Visit:

Before the screening takes place, potential subjects for the trial will be provided with written and oral information about the trial and the procedures involved. Subjects must sign the informed consent form (ICF) prior to entering the study. Please see section 9.1.1 for further details.

The screening visit will be performed up to 28 days prior to the first dosing day, to identify eligible subjects for the study. All assessments performed at the screening visit are stated in Table 16-1 and will be recorded in the electronic case report form (eCRF). Please see section 9.1.2 and 11.2 for further details.

In-house Period:

Subjects will check in to the clinical research unit (CRU) in the morning of Day -2 for a 9-day in-house period. They will receive standardized meals throughout their in-house stay. A 12-lead standard ECG will be performed. Subjects will be connected to an ABPM system for measurement of blood pressure (BP), and measurements will be started overnight on Day -2 to familiarize the subjects with the device. Measurements will continue until the morning of Day 4.

In the morning of Day -1, subjects will get connected to a Holter ECG for continued measurement of the heart rate activity until the morning of Day 4.

Only 24-hour monitoring data from Day -1 to Day 1 will be used for the monitoring evaluation as baseline assessments for ABPM and Holter ECG monitoring. For measuring timepoints, please see sections 9.1.14 and 9.1.15.

Subjects will be randomized to a single SC injection of HM15211 or placebo. Randomization will take place as close to the drug administration as possible.

On Day 1, after an \geq 10 h overnight fast, subjects will be dosed with HM15211or placebo at approximately 08:00 hours (t=0), through SC injection into the abdominal wall by qualified study staff. Measurements of vital signs, ECG, blood sampling for PK and PD analyses, local injection site evaluation, and laboratory parameter will be performed for safety evaluation, at timepoints stated in Table 16-1.

ABPM and Holter ECG monitoring will be continued until the morning of Day 4 for the post-dose evaluation. 24-hour monitoring evaluations will be performed together with available PK data, in order to determine the best time period for 24-h monitoring period around PK_{peak}.

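### On the earliest permitted schedule, the next cohort can be dosed before the stop for a Grade 2 AE lasting more than 7 days can be decided for later-onset events, with no required hold and no explicit step to re-apply the rule

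*Protocol*

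**What the plan says.** Protocol section 6.4.1 lists conditions under which escalation must stop. One is a single-subject criterion: "One subject in a cohort develops an AE Grade 2 toxicity that persists for more than 7 days", where the investigator considers the event related. The list has no end date and is not confined to the review meeting.

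Section 4.5 sets the timing of the decision. Once at least six subjects, at least four of them on HM15211, "in each cohort have completed at least Day 10, safety and available PK data will be reviewed", and the sponsor and investigator then decide on the next dose, which may be up to twice the previous level. Section 4.5 continues: "Following the dose escalation decision, the procedures for the subsequent cohorts will be identical to those described above". Section 6.1 states the same timing: "Cohorts may partially overlap after at least 6 subjects have completed at least D10 and a dose escalation decision has been made". The study summary (section 2.0) agrees: "Cohorts may partially overlap, if dose escalation decision after the Day 10 Visit has been made".

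Three further provisions govern how soon dosing can follow:
- Section 6.2: "Subjects will check in to the clinical research unit (CRU) in the morning of Day -2", with dosing on Day 1.
- Section 6.1, sentinel rule: dosing of "the first 2 subjects (1 on active, 1 on placebo) and the remainder of the cohort at least 24 hours apart".
- Section 6.1, spacing rule: "A minimum of 10-days between the start date of consecutive dose levels will be maintained".

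Section 6.3 predicts Cmax at about 3 days after dosing. Sections 10.4.1 and 10.6 require AEs to be monitored and followed up, but do not connect that follow-up to dosing of the next cohort.

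**The concern.** A criterion that needs more than 168 h of persistence is paired with a review that may take place 216 h after dosing. For much of the reviewed period, an ongoing related Grade 2 event cannot yet have met the criterion at the review. For later onsets it still cannot have met it when the next cohort is dosed.

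A site that follows the text exactly could therefore give up to six further active subjects (one sentinel, then five others) up to twice the dose while the outcome of a fixed stopping criterion in the current cohort is unknown. In a first-in-human study, a point that section 6.4.1 settles by rule would then rest on judgement.

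**Working it through.** **Inputs**
- Persistence needed: more than 7 days = more than 168 h (section 6.4.1).
- Day 10 visit: 216 h, window ±1 day, so 192 to 240 h (section 9.1.6).
- Check-in to dosing: Day -2 to Day 1. The stated 9-day stay ending on Day 7 implies no Day 0 (-2, -1, 1 to 7 is nine days), so the lead time is 48 h.
- Sentinel pair to remainder: at least 24 h (section 6.1).
- Predicted Cmax: about 72 h (section 6.3).

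**Reproducing the plan's own figure.** Hours post-dose = (Day - 1) × 24. Day 10 gives 9 × 24 = 216 h, as stated. Day 17 gives 384 h and Day 30 gives 696 h, also as stated.

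**Formula.** At time t after dosing, the criterion can have been met only if onset < t - 168 h. The table takes the decision and next-cohort check-in on the day of the visit.

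| Time point | Day 9 visit | Day 10 visit | Day 11 visit |
|---|---|---|---|
| Review, t | 192 h | 216 h | 240 h |
| Onset must precede | 24 h | **48 h** | 72 h |
| Sentinel dosing, t = review + 48 | 240 h | 264 h | 288 h |
| Onset must precede | 72 h | **96 h** | 120 h |
| Remainder dosing, t = review + 72 | 264 h | 288 h | 312 h |
| Onset must precede | 96 h | **120 h** | 144 h |

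**Undetermined window, nominal Day 10.** For events begun by the review:
- At sentinel dosing: 216 - 96 = 120 h of the 216 h reviewed.
- At remainder dosing: 216 - 120 = 96 h.

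**Onset at predicted Cmax (72 h), nominal Day 10.**
- At the review it has lasted (216 - 72)/24 = 6.0 days, so the stop is not met.
- At sentinel dosing it has lasted (264 - 72)/24 = 8.0 days, so the stop is met.
- After a Day 9 visit it has lasted exactly (240 - 72)/24 = 7.0 days at sentinel dosing, which is not more than 7.

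**Effect of delay.** Each extra day before dosing adds 24 h to the limit. With five extra days the sentinel limit is 264 + 120 - 168 = 216 h, which covers every event begun before the nominal review.

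**The 10-day spacing rule.** At most two of the six reviewed subjects are sentinels, so at least four were dosed 24 h or more after the cohort start. The next first dose then falls at 24 + 216 + 48 = 288 h from that start, or 24 + 192 + 48 = 264 h with Day 9 visits. Both exceed 240 h, so the spacing rule adds no protection.

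**Subjects at other stages.** The limits are for the last-dosed of the reviewed subjects. The current cohort's sentinels are at least 24 h ahead, so their limits are at least 24 h later. Up to 6 - 4 = 2 active subjects may be short of Day 10. If such a subject was dosed L hours after the last reviewed subject, the limit at sentinel dosing is 96 - L. The protocol gives no value for L; lags of 24 h and 72 h, taken as illustrations, give 72 h and 24 h.

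**The case against.** The strongest reply is that section 6.4.1 is a standing rule. If a related Grade 2 event passes 7 days after the decision but before dosing, the rule already forbids that dosing. This stands. A reader might infer that the stop lapses once the review is over, or that the protocol authorises dosing after the stop has been met. The text supports neither. What is missing is an explicit step at which someone applies the rule again before dosing.

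Second, an event of 7 days or less meets no stop of this kind, so dosing while it is ongoing breaks no rule, and any duration criterion lags behind any fixed cut-off. That is also correct, which makes this a weakness of design and not a contradiction. The lag still matters here because the exposure it allows is a higher dose in new subjects.

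Third, the document history explains the Day 10 cut by expecting dose-limiting events around Cmax. A reader might infer that such events escape the rule. After a nominal Day 10 review they do not: a 72 h onset has met the stop by sentinel dosing, provided someone looks. The undetermined events start a day or more after predicted Cmax. They cannot be dismissed, because the 72 h figure is a prediction. As an illustration, if the human half-life fell within the animal range in section 4.3 (35.7 to 86.0 h), the concentration 24 h after the peak would still be 2^(-24/35.7) = 63% to 2^(-24/86.0) = 82% of it.

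Fourth, other protections exist: one related event of Grade 3 or higher stops escalation at once, similar significant abnormalities in two subjects can stop it, dose steps are capped at two-fold, a single active sentinel goes first, and the sponsor and investigator can stop on tolerability grounds. These limit the consequence. None requires a wait for an undetermined Grade 2 event.

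**Conclusion.** The point holds in a limited form. On the fastest schedule the text allows, the criterion can be met only by onsets before 48 h at the review, 96 h at sentinel dosing and 120 h at remainder dosing. No provision in sections 4.5, 6.1 or 6.4.1 requires dosing to wait for later onsets, or names a point between decision and dosing at which the rule is re-applied.

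The hour limits are not general. They assume that the last reviewed subject is at exactly 216 h, that decision and check-in fall on that day, that check-in follows the decision (as section 4.5 reads), and that duration is counted as elapsed time. Counting days inclusively moves the limits about 24 h later, and so does each day of delay.

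A reader might also conclude that escalation should wait until every event seen at Day 10 has had time to declare itself, which means after 216 + 168 = 384 h (nominal Day 17). The documents do not support that as a general requirement: the criterion concerns only ongoing related Grade 2 events, and a hold limited to those is enough. This is the lowest tier of the stops, so the gap is modest, but it should be closed because the remedy is simple.

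**What to change.** Keep the Day 10 review and add to sections 4.5 and 6.4.1:

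> The 6.4.1 criteria are re-applied to all current-cohort subjects, including those not yet at Day 10, immediately before dosing the next cohort's sentinel pair and again before its remainder. If any related Grade 2 AE is then ongoing with 7 days or less elapsed, dosing waits until it has resolved (stop not met) or has lasted more than 7 days (stop applies).

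Because the check is made at dosing, it also covers events that begin between the review and dosing.

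The cost is an amendment of two sentences. No new type of data is needed, since section 10.6 already requires AE follow-up. As the next scheduled visit after Day 10 is Day 17, the site may have to contact subjects in between to confirm AE status. The hold can delay dosing by up to about a week per event. Staggered events can add up, and an event in a placebo subject, assessed as related under the blind, can also trigger it.
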